### **End of Treatment (EOT)**

The EOT visit occurs within 14 days after the last administration of CB-103. All participating patients must complete this visit even if they have had to prematurely discontinue treatment with CB-103.

### **Safety follow-up period**

All patients will have a safety follow-up for adverse events and serious adverse events 28 days after the last dose of CB-103 after which the end-of-study is reached. The safety follow-up visit must be performed by all patients who have received at least one administration of CB-103. All adverse events and/or serious adverse events occurring

during this period will be recorded in the Adverse Event electronic Case Report Form (eCRF).

### **5.1.2 Study Duration**

The overall study will be completed 28 days after the last patient in Part B of the study received the last treatment.

### **5.1.3 End of Study**

The end-of-study overall is reached when the last patient in Part B has been on study treatment for up to 12 cycles (or after completion of the treatment period in T-ALL/T-LBL patients as defined above) plus the safety follow-up period of 28 days. In case the study is stopped before any patient was treated for 12 months, the end-of-study is reached 28 days after the last patient in Part B of the study has received his/her last dose of CB-103.

If the last patient in Part B of the study remains on treatment for more than 12 cycles for the purposes of generating the Clinical Study Report (CSR), the end of the study will be defined as the point where the last patient enrolled in Part B has had the opportunity to be dosed for up to 12 cycles after 1st CB-103 administration and has completed the safety follow-up/ end-of-study (EOS) visit. Patients on treatment at that time may be eligible to continue treatment with CB-103. The Sponsor reserves the unilateral right, at its sole discretion, to determine whether to supply CB-103, and by what mechanism, after the end of study is reached or termination of the trial and before it is commercially available.

With respect to the Part A of the study, a separate CSR will be prepared and the cut-off for the data to be included in this report will be set after the safety follow-up visit is performed by all patients in Part A of the study, that will occur 28 days after the last dose of CB-103 and the last patient in Part A has been on treatment for a maximum of 6 cycles. An addendum (or addenda) to the CSRs of Part A and Part B may be generated to report the remaining data from patients continuing to be followed up for progression and survival outcome beyond the cycle 6 or cycle 12, respectively.

The study procedures to carry out beyond 6 cycles (Part A) or 12 cycles (Part B) are indicated in the schedule of assessments. Data from these patients will be summarised and reported in a separate, abbreviated CSR.

### **5.1.4 Committees**

#### **5.1.4.1 Cohort Review Committee**

Prior to enrolment of patients into Part A (escalation) of the study, a cohort review committee (CRC) will be established, consisting of the Principal Investigators of at least those sites where the patients are enrolled, Sponsor CMO/designee and representatives, CRO representatives (e.g. medical monitor, statistician) and independent experts as required (e.g. cardiology expert). The CRC will oversee safety, cohort evaluation, dose escalation and the evaluation of MTD/RP2D for the study. A formal charter which will

establish the rules, meeting frequency and scope of responsibilities of the CRC will be prepared prior to the start of the study.

For the review of a dose level by the CRC, there will be at least 3, up to 6 patients evaluable for DLT. The CRC will review data from one complete treatment cycle (28 days) for at least 3 patients in the respective dose cohort to authorise dose escalation.

## **5.2 INVESTIGATIONAL SITES**

This is a multi-centre study to be conducted globally in several countries. Additional site(s) may be included for back-up purposes and may be activated if needed.

Administrative and Contact Information, and List of Investigators are provided separately.

## **6. STUDY POPULATION**

This study will include adult male and female patients  $\geq 18$  years. Patients must meet all of the inclusion criteria and none of the exclusion criteria in order to qualify for the study.

Adult patients with locally advanced solid tumour or haematological malignancies (surgically unresectable locally advanced or metastatic solid tumours or haematological malignancies) whose disease has progressed on at least one line of systemic therapy and for whom no standard curative therapy exists will be enrolled into Part A (Phase I dose-escalation). All participants must have histological or cytological evidence for the diagnosis of the respective cancer indication. CB-103 has been shown to cross the blood-brain-barrier in animals. All patients must be in an advanced or metastatic stage of disease after available curative therapies have failed to confer acceptable clinical benefit/risk to their advanced or metastatic cancer. Patients may be enrolled into the study and treated with CB-103 at an earlier line of treatment if they have a tumour with confirmed NOTCH pathway activation assessed by at least one diagnostic method, justifying the treatment with a NOTCH pathway inhibitor in an earlier line of treatment. This will be at the discretion of the Investigator.

When the MTD/RP2D is defined, based on decision of the CRC, the MTD/RP2D confirmatory cohort will open to include approximately 45 additional NOTCH-positive patients with recurrent/metastatic adenoid cystic carcinomas (ACC), breast cancer, r/r T-ALL/T-LBL, or any other solid tumour with proven Notch pathway activation, who will receive the MTD/RP2D dose to ascertain that optimal safety related to efficacy and pharmacodynamics in the tumour and in peripheral blood are achieved.

For the expansion arms in Part B of the study, the following are the preliminary indications for patients with NOTCH activated pathways planned:

1. Adenoid cystic carcinoma (ACC)
2. Triple negative breast cancer (TNBC)
3. Breast cancer (ER+/-, HER2+/-)
4. Osteosarcomas, Malignant glomus tumour
5. GI cancers (resistant to oxaliplatin or irinotecan-based therapy colorectal cancer, hepatocellular carcinoma)
6. r/r T-ALL/T-LBL
7. Any other cancer (haematologic or solid) with confirmed Notch pathway activation (basket arm)

The preliminary indications considered for the expansion arms may be adapted and modified based on the results of Part A of this study as well as from the outcome of future *in vivo* pharmacology studies with CB-103. All the adaptations will result in a protocol amendment.

## 6.1 RECRUITMENT PROCEDURES

Patients will be recruited primarily from investigational site/country clinical databases; however, in some cases, potential patients may be identified prior to consenting to take part in this study using pre-screening enrolment logs, Independent Ethics Committee (IEC)/Institutional Review Board (IRB) approved newspaper/radio advertisements and mailing lists.

### 6.1.1 Inclusion Criteria

Patients must meet the following criteria for study entry:

#### 1. Disease

- a. Histologically or cytologically confirmed solid tumours that are surgically unresectable, locally advanced, or metastatic, which have progressed on at least one line of systemic therapy (with the exception of ACC patients who are allowed to be systemic treatment-naïve) and for which no established therapeutic alternatives exist.

or

- b. Relapsed or refractory (r/r) T-ALL or T-LBL. Refractory patients are defined as T-ALL/T-LBL patients with  $\geq 5\%$  bone marrow blasts and/or concomitant extramedullary involvement, who have not achieved a CR after standard induction/consolidation therapy attempt. Relapsed patients are defined as T-ALL/T-LBL patients who have recurrent disease, i.e.  $\geq 5\%$  bone marrow blasts and/or concomitant extramedullary relapse, after having achieved a prior CR.
- c. For **Part A (dose-escalation)** solid tumour indications based on known frequent involvement of the NOTCH pathway activation in these indications, and tumours with an *a priori* known NOTCH1-4 pathway activation are also eligible, as defined below:
  - Breast cancer (TNBC, ER+/-, HER2+/-), GI cancers (resistant to oxaliplatin or irinotecan-based therapy colorectal cancer, hepatocellular carcinoma), osteosarcoma, ACC and malignant glomus tumour.
  - Any other solid cancer (including lymphoma) with a confirmed NOTCH1-4 activating mutation or genetic lesion.
- d. For **Part A (MTD/RP2D confirmatory cohort) and Part B expansion cohorts**, solid and haematological tumour indications with confirmed Notch pathway activation as follows:
  - ACC
  - Metastatic breast cancer (regardless of receptor status of ER/PR, HER2)
  - r/r T-ALL/T-LBL
  - Any other cancer (haematologic or solid) with a confirmed NOTCH pathway activation, after approval by the Sponsor

---

CONFIDENTIAL

May not be used, divulged, published, or otherwise disclosed without the consent of Cellestia Biotech AG

Notes:

- Patients are eligible if Notch pathway activation was determined in the past. If the Notch status is unknown, it will be determined on fresh bodily material.
  - The pathogenic character of the detected mutation/genetic alteration needs to be confirmed before the patient can be enrolled. Patients whose tumour mutations/alterations are not unambiguously pathogenic will be included at the Sponsor's discretion. Details on molecular alterations as signs of Notch pathway activation and the specific test method can be found in the laboratory manual.
- e. Patients with solid tumours must have at least one measurable lesion (at least 1.0 cm in diameter) according to RECIST v1.1 guideline for solid tumours (irradiated lesions are only measurable if unequivocal disease progression is demonstrated).
- f. **Patients with solid tumour indications in Part A (dose-escalation):**
- Sufficient archival tumour tissue samples. If the archival tissue is older than 6 months at screening – or, if not available – a fresh pre-dose tumour biopsy is required. If the lesion is not accessible for a fresh tumour biopsy, a liquid biopsy may be used after confirmation with the Sponsor.
- g. **Patients with solid tumours in the MTD/RP2D confirmatory cohort of Part A and in Part B:**
- If the Notch status is unknown, patients with solid tumours should have sufficient archival biopsy tissue not older than 6 months prior to pre-screening (or, if not available, a fresh tumour biopsy must be taken) in order to enable the selection of the patients.
- All solid tumour patients: tumour lesions accessible to biopsy and patient willing to provide a fresh tumour biopsy at pre-dose, one during treatment, and one at disease progression or when clinically indicated. In individual cases where the lesion is not accessible for a fresh tumour biopsy, a liquid biopsy may be used after confirmation with the Sponsor.
- h. Life expectancy of at least 3 months in the opinion of the investigator.

## 2. Demography

- a. Men and women  $\geq$  18 years old on the day of signing informed consent.
- b. Eastern Cooperative Oncology Group (ECOG) performance status 0 or 1.
- c. Patients able and willing to swallow capsules.

### 3. Organ function and laboratory results

Patients must have the following laboratory values (obtained within 14 days of enrolment):

- a. Total serum bilirubin  $\leq 1.5 \times$  upper limit of normal (ULN)
- b. Alkaline phosphatase (ALP)  $\leq 2.5 \times$  ULN; if liver function abnormalities are due to the underlying malignancy and known bone metastases, then ALP must be  $\leq 5 \times$  ULN
- c. Serum aspartate aminotransferase (AST/SGOT) and alanine aminotransferase (ALT/SGPT)  $\leq 2.5 \times$  ULN; if liver function abnormalities are due to the underlying malignancy and known hepatic metastases, then AST and ALT must be  $\leq 5 \times$  ULN
- d. Serum creatinine  $\leq 1.5 \times$  ULN; or if serum creatinine  $> 1.5 \times$  ULN, then serum creatinine clearance (CrCl)  $\geq 50$  mL/min (estimated by Cockcroft-Gault formula)
- e. Potassium levels within normal limits or correctable with supplements
- f. Total calcium levels (corrected for serum albumin) within normal limits or correctable with supplements
- g. Magnesium levels within normal limits or correctable with supplements
- h. Phosphorus levels within normal limits or correctable with supplements
- i. Serum albumin concentration  $\geq 30$  g/L
- j. Patients with solid tumours must have:
  - Absolute neutrophil count (ANC)  $\geq 1.5 \times 10^9/L$
  - Haemoglobin (Hgb)  $\geq 10$  g/dL ( $\geq 100$  g/L)
  - Platelet count  $\geq 75 \times 10^9/L$  (without platelet transfusion or growth factor support in the preceding 7 days)
  - Partial thromboplastin time (PTT)  $\leq 1.5 \times$  ULN and international normalised ratio (INR)  $\leq 1.3$  (unless the patient is receiving therapeutic anticoagulants)

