## **INCLUSION/EXCLUSION CRITERIA**

### **Inclusion criteria**

Patients must meet the following criteria for study entry:

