## 3. Organ function and laboratory results

Patients must have the following laboratory values (obtained within 14 days of enrolment):

- a. Total serum bilirubin  $\leq 1.5$  x upper limit of normal (ULN)
- b. Alkaline phosphatase (ALP)  $\leq 2.5$  x ULN; if liver function abnormalities are due to the underlying malignancy and known bone metastases, then ALP must be  $\leq 5$  x ULN

- c. Serum aspartate aminotransferase (AST/SGOT) and alanine aminotransferase (ALT/SGPT)  $\leq 2.5 \times \text{ULN}$ ; if liver function abnormalities are due to the underlying malignancy and known hepatic metastases or bone metastases, then AST and ALT must be  $\leq 5 \times \text{ULN}$
- d. Serum creatinine  $\leq 1.5 \times \text{ULN}$ ; or if serum creatinine  $> 1.5 \times \text{ULN}$ , then serum creatinine clearance (CrCl)  $\geq 50 \text{ mL/min}$  (estimated by Cockcroft-Gault formula)
- e. Potassium levels within normal limits or correctable with supplements
- f. Total calcium levels (corrected for serum albumin) within normal limits or correctable with supplements
- g. Magnesium levels within normal limits or correctable with supplements
- h. Phosphorus levels within normal limits or correctable with supplements
- i. Serum albumin concentration  $\geq 30 \text{ g/L}$
- j. Patients with solid tumours must have:
  - Absolute neutrophil count (ANC)  $\geq 1.5 \times 10^9/\text{L}$
  - Haemoglobin (Hgb)  $\geq 10 \text{ g/dL}$  ( $\geq 100 \text{ g/L}$ )
  - Platelet count  $\geq 75 \times 10^9/\text{L}$  (without platelet transfusion or growth factor support in the preceding 7 days)
  - Partial thromboplastin time (PTT)  $\leq 1.5 \times \text{ULN}$  and international normalised ratio (INR)  $\leq 1.3$  (unless the patient is receiving therapeutic anticoagulants)

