### **8.1.1 Eligibility Screening**

Patients are allowed to enter the study based on confirmation of the eligibility criteria (refer to inclusion and exclusion criteria in Section 6.1.1 and Section 6.1.2) at screening/baseline.

The procedures for eligibility check, patient identification number assignments and coordination among the investigational site involved will be provided in a separate document prior to study start.

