## **8.10 TIMING OF STUDY ASSESSMENTS**

### **8.10.1 Screening and Pre-treatment Assessments**

Written informed consent for participation in the study must be obtained before performing any study-related procedures. The ICFs for enrolled patients and for patients who are not subsequently enrolled will be maintained at the investigational site.

All screening and pre-treatment assessments must be completed and reviewed to confirm that patients meet all eligibility criteria. The Investigator will complete the Eligibility Check List form after completing the screening procedures as detailed in the Patient Registration Plan.

Screening, baseline and pre-treatment assessments will be performed between 1 to 28 days prior to Day 1 (according to the Schedule of Assessments in [Appendix 1](#) and [Appendix 2](#)). Patients cannot commence the enrolment procedure until all the entry criteria have been fulfilled. Where the clinical significance of an abnormal screening test result (laboratory or any other tests) is considered uncertain, the test should be repeated to confirm the result.

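### Inclusion criterion 3c gives two AST/ALT entry limits for patients with bone but no liver metastases: 5 x ULN in the synopsis, 2.5 x ULN in section 6.1.1

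*Protocol*

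**What the plan says.** The protocol prints its inclusion criteria twice, in the synopsis and in section 6.1.1. Both lists open with "Patients must meet the following criteria for study entry" and both introduce criterion 3 with "Patients must have the following laboratory values (obtained within 14 days of enrolment".

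Criterion 3c sets AST and ALT at no more than 2.5 x ULN, with a higher limit of 5 x ULN for some patients. The condition for the higher limit differs:

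- Synopsis: "if liver function abnormalities are due to the underlying malignancy and known hepatic metastases or bone metastases, then AST and ALT must be" at or below 5 x ULN.
- Section 6.1.1: "if liver function abnormalities are due to the underlying malignancy and known hepatic metastases, then AST and ALT must be" at or below 5 x ULN.

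Section 8.1.1 (Eligibility Screening) tells the reader to "refer to inclusion and exclusion criteria in Section 6.1.1 and Section 6.1.2". Section 8.10.1 adds that "Patients cannot commence the enrolment procedure until all the entry criteria have been fulfilled".

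**The concern.** An entry limit on liver enzymes should have one value, and here one identifiable group of patients has two. A site working from the synopsis could enrol a patient whom section 6.1.1 excludes. SAP section 5.3.1 lists patients who do not comply with the inclusion criteria, so whether such a patient appears there as a violation depends on which wording is applied.

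The liver matters in this trial. Protocol section 2.5.4 names it as a target organ in rats and dogs. Section 2.5.6 reports that the one serious adverse event considered drug-related up to August 2020 was drug-induced liver injury. That patient had extensive liver involvement, so the case shows that hepatic safety is relevant here but says nothing about patients with bone metastases only.

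**Working it through.** The check is a comparison of texts. The only arithmetic is the ratio of the two limits.

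**Step 1: how far the lists differ.** Criterion 3 has ten items, a to j. Nine of them (a, b and d to j) carry the same limits in both lists. Only 3c differs.

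**Step 2: AST/ALT limit by patient type, for abnormalities attributed to the malignancy.**

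| Known metastases | Synopsis 3c | Section 6.1.1 3c |
|---|---|---|
| Liver, with or without bone | 5 x ULN | 5 x ULN |
| Bone, no liver | 5 x ULN | 2.5 x ULN |
| Neither | 2.5 x ULN | 2.5 x ULN |

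Only the middle row conflicts. The ratio of the limits is 5 / 2.5 = 2, and the disputed range is AST or ALT above 2.5 and up to 5 x ULN.

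**Step 3: which wording fits the rest of the protocol.** Three features favour section 6.1.1, although none settles what was intended.

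- Section 8.1.1 cites sections 6.1.1 and 6.1.2 for the eligibility check, not the synopsis.
- In section 6.1.1 bone metastases relax the ALP limit (3b: "if liver function abnormalities are due to the underlying malignancy and known bone metastases, then ALP must be" at or below 5 x ULN) and liver metastases relax the AST/ALT limit (3c). The synopsis has the same 3b, so this is suggestive only.
- The recovery allowances in section 7.4.6.1.3 and in the grade 3 AST/ALT row of Table 6 are given for liver metastases only.

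**Step 4: what follows if the synopsis wording is used.** Table 6 places AST/ALT above 3 and up to 5 x ULN in grade 2. After a grade 3 rise, dosing is withheld until grade 1 or better, or grade 2 or better with liver metastasis. A patient with bone metastases only, admitted at above 3 to 5 x ULN, who then had such a rise would have to fall to 3 x ULN or below, which is lower than the entry value, before restarting. According to section 7.4.5 these rules apply to toxicities not clearly attributed to disease, so this would arise only for a rise not clearly put down to the cancer.

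**The case against.** The strongest reply is that the protocol already yields one operative answer. Section 8.1.1 sends the reader to section 6.1.1. Where the synopsis is meant to govern, the protocol says so: section 7.4.4 for the DLT criteria and section 7.5.2 for prohibited medication. And if both lists must be met, as section 8.10.1 implies, the stricter limit binds. Either route gives 2.5 x ULN. Sites also work from a checklist: "The Investigator will complete the Eligibility Check List form after completing the screening procedures as detailed in the Patient Registration Plan".

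The affected group may also be close to empty. It needs bone but no liver metastases, transaminases in the disputed range, attribution to the malignancy, and every other criterion met, including bilirubin no higher than 1.5 x ULN. The sponsor already accepts 5 x ULN for patients with liver metastases, and the hepatic DLT criteria, the dose rules and the Hy's law reporting apply to everyone.

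Much of this stands. The reference in section 8.1.1 lowers the practical risk, the group is narrow, and the two-fold ratio describes the limits and not the impact. It does not remove the contradiction. The references in sections 7.4.4 and 7.5.2 also show that sites are expected to use the synopsis as working text, and the protocol gives no general order of precedence. The checklist is not among the documents, so its wording is unknown. The objection is also right that the intended wording is inferred, which is why the fix leaves the sponsor a choice.

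**Conclusion.** The inconsistency is real and confined to criterion 3c. For patients with bone but no liver metastases, the AST/ALT limit is 5 x ULN in the synopsis and 2.5 x ULN in section 6.1.1. The text favours section 6.1.1 but does not say which wording was meant.

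This is a minor point. The documents do not say how many patients fall in the disputed range, and no estimate is offered. The sample size, the dose-escalation model, the endpoints and the analysis sets are unaffected. The consequences are limited to who may be enrolled at the margin and who is listed as an inclusion violation. The conclusion rests only on the current wording of the two lists.

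**What to change.** Delete the reference to bone metastases from criterion 3c in the synopsis so that it matches section 6.1.1. This removes three words and can wait for the next amendment. The Eligibility Check List should be checked at the same time to confirm that it carries the section 6.1.1 wording.

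If the sponsor intends to admit patients with bone metastases only at up to 5 x ULN, add bone metastases to 3c in section 6.1.1 instead. In that case the recovery allowances in section 7.4.6.1.3 and in the grade 3 row of Table 6 should be extended to those patients, making three wording changes. That extension is advisable but not needed to resolve the inconsistency itself.
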